TITLE PAGE –NON-INTERVENTIONAL STUDY INFORMATION

PROTOCOL TITLE	Post Authorization RIXUBIS Study (PARIXS)
PROTOCOL ID #	251401
ORIGINAL	20 MAR 2015
EU PAS REGISTER	Study to be registered
MEDICINAL PRODUCT	
Active Ingredient(s)	Recombinant Factor IX (FIX)
Medicinal Product	Recombinant Factor IX (RIXUBIS)
MARKETING AUTHORIZATION HOLDER (MAH)	Baxalta Innovations GmbH, [name]
JOINT PASS	No
RESEARCH QUESTION & OBJECTIVES	
Research Question	

The study addresses the description of routine clinical practice with a new rFIX product (RIXUBIS) using any therapeutic regimen administered to hemophilia B patients.
 
This post-authorization, prospective, uncontrolled, observational, open-label, non-interventional, multicenter cohort study is designed to measure short and long-term outcomes in terms of effectiveness, safety, joint health, quality of life and economic outcomes in routine clinical practice.
	
Primary Objective	
To assess hemostatic effectiveness in the prevention of bleeding events in subjects with hemophilia B receiving rFIX (RIXUBIS) using any therapeutic regimen in routine clinical practice.	
Secondary Objective(s)	

 • To describe hemostatic effectiveness in the treatment of bleeding events in subjects with hemophilia B receiving rFIX (RIXUBIS). • To describe the safety and immunogenicity in subjects with hemophilia B receiving rFIX (RIXUBIS). • To describe joint health outcomes in subjects receiving rFIX (RIXUBIS). • Health-Related Quality of Life (HR-QoL) objectives: 
 ➤ To describe HR-QoL in subjects receiving rFIX (RIXUBIS) ➤ To describe acute and chronic pain associated with hemophilia in subjects receiving rFIX (RIXUBIS) ➤ To describe the physical activity in subjects receiving rFIX (RIXUBIS) • To describe hemophilia-related comorbidity in subjects receiving rFIX (RIXUBIS) • To describe healthcare resource use in subjects receiving rFIX (RIXUBIS) on-demand or prophylactically 	
COUNTRY(-IES) OF STUDY	Germany, with the option to expand to other countries

AUTHOR	[name] Associate Medical Director Global Medical Affairs – Hemophilia Baxalta Innovations GmbH [name] P : [contact] - [name] F [contact] M: [contact] – [name] [contact]
---------------	--

MARKETING AUTHORIZATION HOLDER(S)

MAH	Baxalta Innovations GmbH, [name]
MAH CONTACT PERSON	[name] Vice President Global Clinical Development Baxalta Innovations GmbH

SERIOUS ADVERSE EVENT REPORTING

The investigator will comply with applicable laws/requirements for reporting serious adverse events (SAEs) to the ethics committee(s) (ECs).

**ALL SAEs ARE TO BE REPORTED ON THE
SERIOUS ADVERSE EVENT REPORT (SAER) FORM AND
TRANSMITTED TO THE MAH
WITHIN 24 HOURS AFTER BECOMING AWARE OF THE EVENT**

See SAER form for contact information.

Further details are also available in the study team roster.

NON-SERIOUS ADVERSE EVENT REPORTING

Any non-serious adverse events (AEs), all therapies/procedures to treat the AEs, and the outcome of the AEs are to be reported to the MAH on the appropriate case report forms (CRFs) within 5 business days.

ADVERSE EVENT DEFINITIONS AND ASSESSMENT

For information on the definitions and assessment of these events refer to: definitions of AE in Section [11.1.1](#), and assessment of AEs in Section [11.1.2](#), SAE in Section [11.1.1.1](#),

2. LIST OF ABBREVIATIONS

Abbreviation	Definition
AE	Adverse event
ABR	Annualized bleeding rate
AJBR	Annualized joint bleeding rate
aPTT	Activated partial thromboplastin time
AUC	Area under the curve
BU	Bethesda Unit
BW	Body weight
BP	Bodily pain
CHO	Chinese hamster ovary
CRF	Case report form
DIC	Disseminated intravascular coagulation
EC	Ethics committee
e-CRF	Electronic case report form
ED	Exposure day(s)
EFAS	Effectiveness Full Analysis Set
ESODPT	Effectiveness of switch from on demand to prophylaxis
ER	Emergency room
EQ-5D	EuroQol Five Dimension
EQ-5D-Y	EuroQol Five Dimension Youth version
FISH	Functional Independence Score in Hemophilia
FVIII	Factor VIII
FIX	Factor IX
FSI	First subject in
GH	General Health
GPV	Global Pharmacovigilance
HAL	Hemophilia Activity List
HJHS	Hemophilia Joint Health Score
HRQoL	Health-Related Quality of Life
HRQoL AS	Health-Related Quality of Life analysis set
HRUR	Health resource use related
ICF	Informed consent form
IP	Investigational product
IR	Incremental recovery
ITI	Immune tolerance induction
IU	International unit
JHFAS	Joint Health/Function analysis set
LSO	Last subject out

Abbreviation	Definition
MBR	Monthly bleed rate
MRI	Magnetic resonance imaging
MAH	Marketing authorization holder
MCS	Mental Component Summary
MedDRA	Medical Dictionary for Regulatory Activities
NMC	Non-medical complaint
NRS	Numerical rating scale
NSAE	Non-serious adverse event
PEAS	Pharmacoeconomic analysis set
PedHAL	Pediatric Hemophilia Activity Level
PCS	Physical Component Summary
PD	Pharmacodynamics, Pharmacodynamic
PHS	Physical Summary (SF-10)
PK	Pharmacokinetics, Pharmacokinetic
PSS	Psychosocial Summary (SF-10)
PSUR	Periodic Safety Update Report
PTP	Previously treated patient
PUP	Previously untreated patient
QoL	Quality of life
RoM	Range of motion
RP	Role Physical
SAE	Serious adverse event
SAER	Serious adverse event report
SAP	Statistical analysis plan
SAS	Safety analysis set
SIC	Subject identification code
SF	Social Functioning
SF-10	Short-Form-10 Health Survey
SF-12	Short-Form-12 Health Survey
SF-36	Short-Form-36 Health Survey
T1/2	Half-life
TAE	Thrombotic adverse event
VAS	Visual Analog Scale
vs.	Versus
VT	Vitality
WFH	World Federation of Hemophilia
WHO	World Health Organization

3.2 Investigators

The names and contact information of all investigators will be maintained by the MAH in a separate file and provided to the individual investigators (see Annex [14.1](#)).

3.3 Other Individuals Involved in the Study

The names and contact information of other individuals involved with the study (eg, MAH's medical expert, MAH's representative(s), laboratories, steering committees, and oversight committees (including ethics committees [ECs]), as applicable) will be maintained by the MAH and provided to the investigators (see Annex [14.1](#)).

4. ABSTRACT

Title: Post Authorization RIXubis Study (PARIXS)

Rationale and background: The results derived from the RIXUBIS clinical development program suggest that RIXUBIS is efficacious, safe, and well-tolerated in adults and pediatric subjects with severe to moderately severe hemophilia B in a variety of clinical settings ^{1,2,3}.

Research question and objectives:

This study will collect data on a new product rFIX (RIXUBIS) using any therapeutic regimens administered to patients with hemophilia B in routine clinical practice.

The purpose of this study is to measure short and long-term outcomes in terms of effectiveness, safety, joint health and quality of life in routine clinical practice.

The primary objective aims to describe hemostatic effectiveness in the prevention of bleeding events in subjects with hemophilia B receiving rFIX (RIXUBIS) using any therapeutic regimen in routine clinical practice.

The secondary objectives focus on a) the description of the hemostatic effectiveness in the on-demand treatment of bleeding events, and b) safety, immunogenicity, joint-health outcomes, quality of life outcomes including acute and chronic pain and hemophilia B-related co-morbidity, physical activity and health care resources used by subjects receiving rFIX (RIXUBIS) using any therapeutic regimen in routine practice.

Study design: This study is a post-authorization, prospective, uncontrolled, non-interventional, multicenter cohort study to describe the short and long-term effectiveness, safety, immunogenicity, joint health, QoL and pain outcomes, and healthcare resource utilization in subjects with hemophilia B receiving rFIX (RIXUBIS) using any therapeutic regimen, in routine clinical practice.

Population: All patients with congenital hemophilia B receiving RIXUBIS in routine clinical practice. The observation period for each enrolled subject will be 4 years.

Variables: Effectiveness of prophylaxis, effectiveness of on demand treatment, safety and immunogenicity, joint health outcomes, health related quality of life questionnaires, acute and chronic pain assessment, assessment of physical activity, economic variables and comorbidities will be assessed.

Data sources: Data sources are patient's original clinical records and the patient's diary.

Study size: As no hypothesis testing or interval estimation will be applied, the sample size for the study is not based on statistical considerations. The sample size of approximately 80 evaluable subjects was selected as a reasonable number for a non-interventional study to recruit in Germany within the enrollment period planned for the study. Sample size could increase as other countries may participate in this study.

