9. RESEARCH METHODS

9.1 Study Design

This study is a post-authorization, prospective, uncontrolled, non-interventional, multicenter cohort study. Approximately 80 subjects with congenital hemophilia B will be enrolled. Subjects must be prescribed rFIX (RIXUBIS) by the treating physician before study participation. Data will be collected over a period of 4 years from the time of study enrollment. The treating physician will determine the treatment regimen, as well as the frequency of laboratory, radiological, and clinical assessment according to her/his routine. Data will be collected on routinely scheduled and emergency visits. There is no binding visit schedule, however it is recommended that the subjects have at least annual visits. Available data from these visits shall be transcribed onto the electronic case report forms (e-CRFs).

It is considered standard practice for subjects with hemophilia to maintain a diary either on paper or in an electronic form (e.g. Smart Medication) which captures FIX treatment and disease related data. A subject diary will be provided to each subject to assist with the standardization of data collection as stated in Section 9.4.2. Nevertheless, the completion of the diary is a voluntary effort by the individual subject or subject's legally authorized representative. All bleeding events and their treatment recorded in subject diaries during study participation period will be transcribed onto e-CRFs.

QoL questionnaires will be provided at baseline and on an annual basis to subjects or their legally authorized representatives.

As no hypothesis testing or interval estimation will be applied, the sample size for the study is not based on statistical considerations.

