9.2.2 Duration of Study Period(s) and Subject Participation

The overall duration of the study is expected to be 7 years from study initiation (i.e. first subject enrolled) to study completion. The recruitment period is planned to be approximately 3 years. The subject participation period for each individual subject is planned to be 4 years from enrollment to study completion (i.e. last study visit) unless prematurely discontinued.

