9.7 Data Analysis

9.7.1 Datasets and Analysis Cohorts

The effectiveness analysis will be carried out on the primary and secondary endpoints of the study for the following treatment regimens:

- Standard prophylaxis
- On-demand treatment
- Episodic prophylaxis
- ITI

Effectiveness of switch from on-demand to prophylaxis dataset (ESODTP)

Evaluation of effectiveness (ABR, AJBR) after switch from on-demand regimen to prophylaxis in moderate moderately severe and severe hemophilia B patients.

Safety Analysis Set (SAS)

The SAS will consist of data for all subjects who were enrolled, met all inclusion and none of the exclusion criteria, and received at least 1 infusion of FIX (RIXUBIS). If 2 or more AEs are reported together as a unit, the individual Medical Dictionary for Regulatory Activities (MedDRA) preferred terms will be counted as separate events.

Effectiveness Full Analysis Set (EFAS)

The EFAS will consist of data from all subjects who were enrolled, met all inclusion and none of the exclusion criteria. This dataset will be used for the primary effectiveness analysis for the comparison of annualized bleeding rates (ABR, AJBR) between each independent treatment regimen (i.e., prophylaxis, on-demand).

Calculation of Annualized Bleeding Rates (ABR) and monthly Bleeding Rate (MBR)

The ABR will be calculated as follows: $(\text{total number of bleeding episodes} \div \text{observed treatment period in days}) * 365.25$. The monthly bleeding rates (MBR) will be calculated as follows: $(\text{total number of bleeding episodes} \div \text{observed treatment period in days}) * 30.5$. The treatment period for surgeries will be excluded from the bleed rate calculation.

Bleeding occurring prior to the first prophylactic infusion will not be included in the estimation of bleeding rate. The observation period for the on-demand regimen will commence on the day of enrollment (met all inclusion and none of the exclusion criteria); the period for prophylaxis will commence at the first prophylactic infusion once enrolled (met all inclusion and none of the exclusion criteria).

Minimal Observed Treatment Period to Estimate ABR

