9.7.3.4.2 Methods of Analysis for Safety Endpoints

The analysis of AEs will be descriptive. All AEs will be categorized according to the MedDRA dictionary and summarized by system organ class and preferred term. AEs for which the investigator does not state the relationship to RIXUBIS administration will be included. All AEs will be cross-tabulated for relatedness, seriousness, and severity.

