11. MANAGEMENT AND REPORTING OF ADVERSE EVENTS/ADVERSE REACTIONS

11.1 Adverse Events

Each AE from the point of enrolment until study completion will be described on the AE e-CRF using the medical diagnosis (preferred), or, if no diagnosis could be established at the time of reporting the AE, a symptom or sign, in standard medical terminology in order to avoid the use of vague, ambiguous, or colloquial expressions (see definitions in Section 11.1.1). Each AE will be evaluated by the investigator for:

- Seriousness as defined in Section 11.1.1.1
- Severity as defined in Section 11.1.2.1
- Causal relationship to medicinal product exposure as defined in Section 11.1.2.2

For each AE, the outcome (ie, recovering/resolving, recovered/resolved, recovered/resolved with sequelae, not recovered/not resolved, fatal, unknown) and action taken (ie, dose increased, dose not changed, dose reduced, drug interrupted, drug withdrawn, not applicable, or unknown) will also be recorded on the AE e-CRF. Recovering/resolving AEs will be followed until resolution, medically stabilized, or 30 days after the study completion/termination visit, whichever comes first.

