11.1.1 Definitions

An AE is defined as any untoward medical occurrence in a subject administered a medicinal product that does not necessarily have a causal relationship with the treatment. An AE can therefore be any unfavorable and unintended sign (eg, an abnormal laboratory finding), symptom (eg, rash, pain, discomfort, fever, dizziness, etc.), disease (eg, peritonitis, bacteremia, etc.), or outcome of death temporally associated with the use of a medicinal product, whether or not considered causally related to the medicinal product

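### Safety events are counted from consent to study completion with no tie to time on RIXUBIS, so AEs and inhibitors arising after a change of FIX product enter the RIXUBIS incidences

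*Protocol*

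**What the plan says.** The safety objective (title page and Section 8.3) is "To describe the safety and immunogenicity in subjects with hemophilia B receiving rFIX (RIXUBIS"). The time frame comes from several places:

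- **Length of observation.** The abstract says "The observation period for each enrolled subject will be 4 years". Section 9.1 says "Data will be collected over a period of 4 years from the time of study enrollment". Section 9.2.2 says that participation "is planned to be 4 years from enrollment to study completion (i.e. last study visit) unless prematurely discontinued".
- **Start.** Section 9.2.4 treats a patient as enrolled once consent is given. Entry requires a RIXUBIS prescription (Sections 9.1 and 9.2.3.1), not a prior infusion. Section 9.2.6 allows zero as the number of RIXUBIS exposure days at screening.
- **AE recording.** Section 11.1: "Each AE from the point of enrolment until study completion will be described on the AE e-CRF". Section 11.1.2 repeats this, with withdrawal as an alternative end point.
- **AE definition.** Section 11.1.1: "any untoward medical occurrence in a subject administered a medicinal product".
- **Safety set.** Section 9.7.1 takes enrolled, eligible subjects who "received at least 1 infusion of FIX (RIXUBIS").
- **Analysis.** Section 9.7.3.4.2: "All AEs will be cross-tabulated for relatedness, seriousness, and severity". Section 11.1.2 lists two kinds of event to be left out of the AE analysis: bleeds that are not serious adverse events (SAEs), and planned surgery for an unworsened preexisting disease.
- **Endpoints.** Section 9.3.2.2 asks for inhibitor incidence by treatment history and FIX level, and for the incidence of all and of therapy-related SAEs and non-serious AEs. It gives no exposure window.
- **Leaving the study.** Sections 9.2.7 and 9.3.7 name subject choice, loss to follow-up, an AE, termination by the sponsor, investigator decision and other reasons. Stopping or replacing RIXUBIS is not named.

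**The concern.** The objective concerns subjects receiving RIXUBIS, but the rules that decide which events are counted refer to enrolment and study completion. The safety set selects subjects and does not select time: after one RIXUBIS infusion, everything recorded for that subject up to study completion belongs to the set. A subject who changes to another FIX concentrate in year 1 and stays under observation contributes up to three further years of events to the RIXUBIS tables.

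Inhibitor incidence is the most sensitive endpoint. Cases will be few, each weighs heavily, and Section 9.3.2.2 gives no therapy-related version of it as it does for AEs. An inhibitor that formed on a replacement product would stand in the RIXUBIS line.

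There is a second, smaller problem at the start of the window. Recording begins at consent, consent may precede the first infusion, and the AE definition assumes that product has been given. Sites could therefore handle the interval before the first infusion differently.

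**Working it through.** The protocol states no incidence or event count that depends on the window, and Section 9.5 says that the sample size is not statistically based. There is no figure to reproduce. The check is a reading of the text, followed by an illustration of scale.

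**Step 1: follow the text for a subject who changes product.** The subject had at least one RIXUBIS infusion, so is in the safety set (9.7.1). Participation continues unless the subject or the investigator ends it (9.2.7). A later AE falls between enrolment and study completion, so it is recorded (11.1, 11.1.2). It is on neither line of the Section 11.1.2 exclusion list, so it is analysed. It appears in the table of all AEs (9.7.3.4.2) and in the incidences of Section 9.3.2.2. No rule stops it at any step.

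**Step 2: compare with the bleeding rates.** Section 9.7.1 starts the prophylaxis bleeding rate at the first prophylactic infusion after enrolment and drops earlier bleeds. A treatment-based start was written for effectiveness and not for safety.

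**Step 3: is a product change foreseeable?** Section 7.1 reports two of 99 development-programme subjects withdrawn after an SAE that required another FIX product. Section 11.1 provides drug withdrawn as an action taken. Section 14.3 defines on-demand treatment as using any factor concentrate.

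**Step 4: scale for AE rates.** Maximum person-time is 80 × 4 = 320 years. Let f be the share of person-time off RIXUBIS and r the ratio of the event rate off RIXUBIS to that on RIXUBIS. Then

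whole-window rate ÷ on-RIXUBIS rate = (1 − f) + f × r.

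Both f and r are assumptions. If a fraction s of subjects changed product at a time uniform over the 4 years, f = s/2, so s of 10%, 20% and 40% give f of 5%, 10% and 20%.

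| f | On-RIXUBIS years, 320 × (1 − f) | r = 0 | r = 0.5 | r = 1 | r = 2 |
|---|---|---|---|---|---|
| 5% | 304 | 0.95 | 0.975 | 1.00 | 1.05 |
| 10% | 288 | 0.90 | 0.95 | 1.00 | 1.10 |
| 20% | 256 | 0.80 | 0.90 | 1.00 | 1.20 |
| 30% | 224 | 0.70 | 0.85 | 1.00 | 1.30 |

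The error can go either way and vanishes when the two rates are equal.

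**Step 5: scale for inhibitors.** Section 7.2 gives a risk of 1-5% in severe hemophilia B. Applied to all 80 subjects, the expected number is 80 × 0.01 = 0.8 to 80 × 0.05 = 4. The chance of at least one is 1 − 0.99^80 = 0.55 to 1 − 0.95^80 = 0.98. One misattributed case moves the crude incidence by 1/80 = 1.25 percentage points, which is 1/4 = 25% of the expected count at the upper end and more below it. This is illustrative only: eligibility extends to a FIX level of 5%, previously treated patients are included, and Section 7.1 reports no inhibitor among 99 subjects.

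**The case against.** **An on-treatment window is often set in the SAP, which is not shown.** That is true, and silence alone would not be a finding. But the protocol is not merely silent: it gives the start and end of recording, an explicit list of what is left out of the AE analysis, and an instruction to tabulate all AEs. A SAP would have to narrow those statements. It also could not recover a stop date that was never collected.

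**The protocol never says that events count regardless of product.** This is also true. The abstract's sentence gives only a length of observation, and its preceding sentence describes the population as patients receiving RIXUBIS. A reader might infer a deliberate choice to count off-product time. The documents do not support that; the result follows from combining sections. Section 9.2.2 allows early exit and an investigator may discontinue a subject who changes product, but leaving this to discretion allows different follow-up from site to site.

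**Events before the first infusion.** A reader might infer that these are all counted. Section 11.1.1 argues against it, because an AE there needs an administered product. What remains is a conflict between that definition and the start at enrolment.

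**Inflation.** A reader might infer that the AE rates are inflated. Adding off-product time can add events to a crude count, but it adds time at risk too, and Step 4 shows that the rate may rise, fall or stay the same.

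**Inhibitors are already attributed.** Section 11.1.1.1 makes a confirmed inhibitor an SAE, so each one receives a causality rating under Section 11.1.2.2 and can enter the therapy-related SAE incidence. It would therefore be wrong to say that attribution is missing. The point that stands is narrower: the inhibitor incidence itself uses neither the rating nor an exposure window.

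**The data are partly there.** Section 9.3.3 records relevant medication throughout, and Section 9.2.6 collects RIXUBIS exposure days since the last visit and dates of regimen change. This would recover many product changes, though no item is dedicated to stopping RIXUBIS or to its replacement.

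**Conclusion.** The concern holds for the period after a change of product. As written, AEs and inhibitors arising on another FIX product count in incidences that the objective ties to subjects receiving RIXUBIS. At the start of the window the finding is only that two statements must be reconciled.

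The size cannot be determined, because the protocol gives no switching rate and no event rates by product. Under the assumed values in Step 4 the distortion of an AE rate runs from none to 30% in either direction. For inhibitors a single case matters, subject to the limits stated in Step 5. Separate reporting of therapy-related events limits the damage, and the primary bleeding endpoint is not affected by this point. It is worth correcting because safety and immunogenicity are stated objectives and the change is small.

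**What to change.** 1. In Sections 9.7.3.4.2 and 9.3.2.2, base the main AE incidences on time from the first on-study RIXUBIS infusion, or from enrolment for subjects already on RIXUBIS, to a pre-specified interval after the last RIXUBIS infusion. List all other AEs separately with the product in use.
2. Do not apply a fixed cut-off to inhibitors. Visits are not binding and are recommended only yearly (Section 9.1), and inhibitor testing follows routine practice (Table 2), so an inhibitor formed on RIXUBIS may be detected long after a change. Report every inhibitor with its last negative test, first positive test and the FIX product or products used between them. The 30 days in Section 11.1.2.2 should not be borrowed as an exposure window: it only prompts the investigator to name an alternative cause.
3. Reconcile the start at enrolment in Sections 11.1 and 11.1.2 with the definition in Section 11.1.1 for subjects with no RIXUBIS exposure at entry.
4. Record the RIXUBIS stop date and the replacement product explicitly on the e-CRF.

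AE collection and SAE reporting stay unchanged, so no event is lost. The cost is about a paragraph of analysis text and one or two e-CRF fields. The main safety table will show slightly fewer events and less exposure time.
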